7.0 Evaluation of Toxicity

Adverse events are reported as per UTMDACC and Leukemia Phase 2-3 studies (Appendix I and Appendix D). Please refer to lenalidomide package insert for a complete list of side effects.

Myelosuppression and associated complications are expected events during leukemia therapy and are part of the treatment success (marrow emptying of leukemic cells). Therefore, myelosuppression and associated complications such as fever, infections, bleeding and related hospitalizations will not be reported as individual ADRs, but will be summarized in the updated and final reports. Only prolonged myelosuppression, as defined by the new NCI criteria specific for leukemia, i.e., marrow cellularity <5% on day 42 or later (6 weeks) from start of therapy without evidence of leukemia, will be reported as an ADR and considered in defining the maximum tolerated dose (MTD) and dose-limiting toxicity (DLT) of particular agents or regimens.

M. D. Anderson (Sponsor) Reporting Requirements for Serious Adverse Events (SAE) and Dose Limiting Toxicities:

Serious Adverse Event (SAE) Definition

A serious adverse event is one that at any dose (including overdose):

- Results in death
- Is life-threatening¹
- Requires inpatient hospitalization or prolongation of existing hospitalization
- Results in persistent or significant disability or incapacity²
- Is a congenital anomaly or birth defect

- Is an important medical event³
- Suspected positive Pregnancy

¹ “Life-threatening” means that the subject was at immediate risk of death at the time of the serious adverse event; it does not refer to a serious adverse event that hypothetically might have caused death if it were more severe.

² “Persistent or significant disability or incapacity” means that there is a substantial disruption of a person’s ability to carry out normal life functions.

³ Medical and scientific judgment should be exercised in deciding whether expedited reporting is appropriate in situations where none of the outcomes listed above occurred. Important medical events that may not be immediately life-threatening or result in death or hospitalization but may jeopardize the patient or may require intervention to prevent one of the other outcomes listed in the definition above should also usually be considered serious. Examples of such events include allergic bronchospasm requiring intensive treatment in an emergency room or at home, blood dyscrasias or convulsions that do not result in inpatient hospitalization, or the development of drug dependency or drug abuse. A new diagnosis of cancer during the course of a treatment should be considered as medically important.

Adverse Drug Reaction Reporting

As Per UTMDACC and Leukemia Phase II-III Studies (Appendix I and D), toxicity will be scored using CTC Version 4.0 for toxicity and adverse event reporting according to the M.D. Anderson guidelines. Hematologic toxicity will be assessed, graded, and summarized according to the 2008 IWCLL Guidelines (See Table IWCLL Guidelines). Adverse events will be documented in the medical record and entered into the case report form according to the Leukemia-Specific Adverse Event Recording and Reporting Guidelines (Appendix D). The Investigator or physician designee is responsible for verifying and providing source documentation for all adverse events and assigning the attribution for each event for all subjects enrolled on the trial.

2008 IWCLL Grading for Hematological Toxicity Grade	Decrease in PLT* or HGB** (nadir) from pretreatment value, %	Absolute neutrophil count (ANC)/l*** (nadir)
0	10%	2000
1	11 – 24%	1500 – < 2000
2	25 – 49%	1000 – < 1500
3	50 – 74%	500 – < 1000
4	75%	< 500

Death occurring as a result of toxicity at any level of decrease from pretreatment will be recorded as grade 5.

* PLT counts must be below normal levels for grades 1-4. If, at any level of decrease, the PLT count is < 20K/l, this will be considered grade 4 toxicity, unless there was severe or life-threatening low initial PLT count (< 20K/l) pretreatment, in which case the patient is not evaluable for toxicity referable to PLT count.

** HGB levels must be below normal levels for grades 1-4. Baseline and subsequent HGB determinations must be performed before any given transfusions.

*** If the ANC reaches <1000/l, it should be judged to be grade 3 toxicity. If the ANC was <1000/l before therapy, the patient is not evaluable for toxicity referable to the ANC.

If any abnormal laboratory result is considered clinically significant, the investigator must provide details about the action taken with respect to the test drug and about the patient's outcome.

Serious Adverse Events Reporting: The principal investigator has the obligation to report all serious adverse events to the University of Texas M. D. Anderson Cancer Center (MDACC) IRB via the Office of Protocol Research within 24 hours.

All deaths during treatment or within 30 days following completion of active protocol therapy must be reported within 24 hours of knowledge regardless of the attribution. SAEs beyond 4 weeks after the end of study drug administration will be reported if thought to be drug related.

Expedited Reporting by Investigator to Celgene

Serious adverse events (SAE) are defined above. The investigator must inform Celgene in writing using a Celgene SAE form or MEDWATCH 3500A form of any SAE within 24 hours of being aware of the event. The written report must be completed and supplied to Celgene by facsimile within 24 hours/1 business day. The initial report must be as complete as possible, including an assessment of the causal relationship between the event and the investigational product(s). Information not available at the time of the initial report (e.g., an end date for the adverse event or laboratory values received after the report) must be documented on a follow-up report. A final report to document resolution of the SAE is required. The Celgene tracking number (RV-XX-PI-###) and the institutional protocol number should be included on SAE reports (or on the fax cover letter) sent to Celgene. A copy of the fax transmission confirmation of the SAE report to Celgene should be attached to the SAE and retained with the patient records.

Pregnancies

Pregnancies and suspected pregnancies (including a positive pregnancy test regardless of age or disease state) of a female subject occurring while the subject is on lenalidomide, or within 28 days of the subject's last dose of lenalidomide, are considered immediately reportable events. Lenalidomide is to be discontinued immediately. The pregnancy, suspected pregnancy, or positive pregnancy test must be reported to Celgene Drug Safety immediately by facsimile or email using the Pregnancy Initial Report Form. The female subject should be referred to an obstetrician-gynecologist, preferably one experienced in reproductive toxicity for further evaluation and counseling.

The Investigator will follow the female subject until completion of the pregnancy, and must notify Celgene Drug Safety immediately about the outcome of the pregnancy (either normal or abnormal outcome) using the Pregnancy Follow-up Report Form. If the outcome of the pregnancy was abnormal (e.g., spontaneous or therapeutic abortion), the Investigator should report the abnormal outcome as an AE. If the abnormal outcome meets any of the serious criteria, it must be reported as an SAE to Celgene Drug Safety immediately by facsimile, or other appropriate method, within 24 hours of the Investigator's knowledge of the event using the SAE Report Form.

All neonatal deaths that occur within 28 days of birth should be reported, without regard to causality, as SAEs. In addition, any infant death after 28 days that the Investigator

suspects is related to the in utero exposure to the IP should also be reported to Celgene Drug Safety immediately by facsimile, or other appropriate method, within 24 hours of the Investigator's knowledge of the event using the SAE Report Form.

Male Subjects

If a female partner of a male subject taking investigational product becomes pregnant, the male subject taking lenalidomide should notify the Investigator, and the pregnant female partner should be advised to call their healthcare provider immediately.

Celgene Drug Safety Contact Information:

Celgene Corporation
Global Drug Safety and Risk Management
[name]
[name]
[name]
[contact]
E-mail: [contact]

Expedited Reporting by Investigator to Celgene

Serious adverse events (SAE) are defined above. The investigator must inform Celgene in writing using a Celgene SAE form or MEDWATCH 3500A form of any SAE within 24 hours of being aware of the event. The written report must be completed and supplied to Celgene by facsimile within 24 hours/1 business day. The initial report must be as complete as possible, including an assessment of the causal relationship between the event and the investigational product(s), if available. Information not available at the time of the initial report (e.g., an end date for the adverse event or laboratory values received after the report) must be documented on a follow-up report. A final report to document resolution of the SAE is required. The Celgene tracking number **RV-CL-CLL-PI-002544**) and the institutional protocol number should be included on SAE reports (or on the fax cover letter) sent to Celgene. A copy of the fax transmission confirmation of the SAE report to Celgene should be attached to the SAE and retained with the patient records.

Celgene Drug Safety Contact Information:

Celgene Corporation
Global Drug Safety and Risk Management
[name]
[name]
[name]
[contact]
E-mail: [contact]

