Lenalidomide is an immunomodulatory agent related to thalidomide. This oral agent induces clinical responses in patients with CLL. Its mode of action is pleiotropic, affecting the bone marrow and tumor microenvironments, angiogenesis, T cell immune synapse dysfunction, antibody production, regulatory T cells numbers and function and other unknown mechanisms. When patients with CLL received lenalidomide as initial treatment of their disease, improvement in serum levels of immunoglobulins (IgG, IgA and IgM) was observed in a subset of patients [9]. We demonstrated that out of 16 patients who had low IgG level (<700 mg/dL) before therapy, 8 patients (50%) showed a normalization of IgG after 15 cycles and another 3 (19%) showed a rise in IgG of >50% from that of baseline. [9]. In a parallel study from the same patient cohort, we showed that treatment with lenalidomide was also followed by normalization of T cell number

and function [10]. Lapalombella and colleagues have also shown that lenalidomide can enhance CD154 expression on CLL cells and enhance antibody producing ability of B cells in vitro and ex vivo further supporting our hypothesis that lenalidomide could have a positive immunomodulatory effect in patients with CLL [11].

Therefore, we propose to conduct a single arm prospective clinical trial to assess the efficacy of lenalidomide in improving immunoglobulin levels and to potentiate antibody responses to immunizations with influenza and pneumococcal vaccination in patients with CLL.

A low dose of lenalidomide, 5 mg, will be administered three times a week with the plan to escalate to daily dosing in the case of no response. The rationale for the low dose is the potential to obtain an immunoresponse while avoiding the risk for myelosuppression. In our previous experience increase in immunoglobulin levels were seen in patients receiving lenalidomide, 5 mg every-other-day.

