8.0 Criteria for Response

Response criteria -

Ig response – Only IgG levels will be considered for response. IgG levels will be measured as mg/dL by nephelometry (normal range 700-1,600 mg/dL). Response will consist of normalization or improvement by 25% of baseline levels at 6 months during therapy.

Response criteria for the immunization –

Quadrivalent Influenza Vaccine (Fluvarix). HI assay was performed as previously described. Samples were assayed at baseline, 4 weeks (+/- 2 week) and 3 months (+/- 3 weeks) post-vaccination. Response or protection to influenza vaccination was defined as > 40 HU or a fourfold increase in HI titer at 4 weeks (+/- 2 week) and 3 months (+/- 3 weeks) post vaccination, against any of the three strains.

Assessment of the functionality of antigen-specific CD8+ and CD4+ T cells will be performed by intracellular cytokine staining for interferon (INF)-g and tumor necrosis factor (TNF)-a and evaluation of CD154 expression and CD107a cytotoxicity. In brief, PBMCs will be thawed and stimulated for 24 hours with or without the seasonal

influenza vaccine [A/Brisbane/59/2007(H1N1)-, A/Brisbane/10/2007 (H3N2)- and B/Florida/30/2008-like strain; CSL Biotherapies, Hattersheim, Germany]. A response will be considered positive if the % of antigen-specific IFN- γ -, TNF- α -, or CD107a-expressing T cells is ≥ 2 -fold higher than background (unstimulated PBMCs) and if there is a minimum of 0.05% antigen-specific T cells (after subtracting the background or FMO fluorescence minus one).

Pneumococcal Polysaccharide Vaccine - Seroconversion will be defined as at least a two fold increase in levels of antipneumococcal capsular polysaccharide (PCP) IgG antibody or achievement of concentration of $>0.5\mu\text{g/ml}$ in anti-pneumococcal capsular polysaccharide antibody titer (against 6 serotypes). They will be measured before, 4 weeks (+/- 2 week) and 3 months (+/- 3 weeks) post vaccination using ELISA and at the end of the study.

Exploratory Endpoints:

1. Infection rates of influenza or Pneumococcal pneumonia will be recorded during the study.
2. Sustained immunoglobulin responses will be recorded along with serological responses to both the vaccines.
3. Sera will be analysed for cytokine levels and properdin levels.

Correlative studies –

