Lenalidomide-related toxicity (defined as any grade 3 or greater non-hematological toxicity) will be monitored using the method of Thall, Simon and Estey [16] and the study will be terminated early if toxicity occurs in more than 40% of patients. Specifically, denoting the probability of toxicity by p , the study will be stopped early if $\text{Prob}(p > 0.40 \text{ data}) > .95$. The above decision criterion will be applied in cohort size of 5. Assuming a beta (.4, .6) priori for p , the above decision criterion implies that we will stop the trial according to the table below. For example, the trial will be terminated if 4 or more patients experienced toxicities among the first 5 patients.

Number of patients	Number of patients with toxicities is at least
5	4
10	7
15	10
20	12
25	15
30	17

The operating characteristics of this study design based on 10,000 simulations are illustrated in Table 2.

Table 2. Operating Characteristics for Toxicity Monitoring Rule.

True toxicity rate	Prob (stop early)	Sample Size 25 th , 50 th and 75 th percentiles
0.20	0.006	35, 35, 35
0.30	0.039	35, 35, 35
0.40	0.152	35, 35, 35
0.50	0.447	10, 35, 35
0.60	0.808	5, 15, 30

For the primary analysis, we will estimate the rate of IgG response along with the 95% confidence interval. As secondary analyses, we will also estimate the rates of Pneumococcus and Influenza seroconversion response, as defined in the response criteria section, and the corresponding 95% confidence intervals. The study will be considered positive in regard to the secondary endpoints if seroconversion is observed in 60% or more of the subjects for at least one of the vaccinations given. Similar method will be used to estimate the rate of influenza or Pneumococcal pneumonia. The duration of IgG response will be estimated using the Kaplan-Meier method. The cytokine levels and serum properdin levels will be summarized using descriptive statistics and will be compared between IgG responders and non-responders using two-sample t-test or Wilcoxon rank-sum test, as appropriate.

Amendments, Deviations, Regulatory

Protocol Amendments

Any amendment to this protocol must be agreed to by the Principal Investigator and reviewed by Celgene. Amendments should only be submitted to IRB after consideration of Celgene review. Written verification of IRB approval will be obtained before any amendment is implemented.

Protocol Deviations

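### Section 7.0 exempts complications of myelosuppression, hospitalizations included, from individual reporting; this conflicts with the 24-hour SAE duties and could leave the toxicity rule with an incomplete count

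*Protocol*

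**What the plan says.** Protocol Section 7.0 states that "myelosuppression and associated complications such as fever, infections, bleeding and related hospitalizations will not be reported as individual ADRs". Instead, such events appear only in summary form in later reports. The reason given is that myelosuppression is expected in leukemia therapy and is a sign that treatment is working. The one exception is prolonged myelosuppression, defined by marrow cellularity below 5% at day 42 or later.

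The SAE definition in the same section includes an event that "Requires inpatient hospitalization or prolongation of existing hospitalization". Under its SAE reporting paragraph, "The principal investigator has the obligation to report all serious adverse events" to the IRB within 24 hours. The investigator must also inform the drug supplier "of any SAE within 24 hours of being aware of the event", and Section 7.0 states this supplier duty twice. None of these rules excepts expected or myelosuppression-related events.

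Section 7.0 also has adverse events documented in the medical record and entered in the case report form (CRF), with attribution for each event. CRF entry follows Appendix D, which is not among the documents available.

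Section 9.0, which the SAP repeats, monitors toxicity "defined as any grade 3 or greater non-hematological toxicity" every 5 patients. It does not say whether an infection or bleed linked to cytopenia counts, or which data feed each look.

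**The concern.** There are three difficulties.

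- **Conflicting instructions.** For a hospitalization related to myelosuppression, one paragraph says to summarize it later and others say to report it within 24 hours. Site staff cannot tell which governs.
- **A rationale from another setting.** Section 2.0 explains the low dose as a way "to obtain an immunoresponse while avoiding the risk for myelosuppression". Success in this trial is an IgG response, not marrow clearance. The exemption also speaks of maximum tolerated dose, although the trial is not dose-finding, and its only exception rests on marrow cellularity, although Sections 5.0 and 6.0 schedule no marrow examination.
- **A possible gap in safety monitoring.** Infection or bleeding of grade 3 or higher would ordinarily be classed as non-hematological. If the 5-patient looks draw on individual adverse drug reaction (ADR) reports, exempted events would not reach them in time, because summaries in updated and final reports are not tied to the looks. Whether a given infection is associated with myelosuppression is itself a judgment, made here in patients with IgG below 500 mg/dl.

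**Working it through.** **Step 1. The texts side by side**, for a patient admitted with an infection during neutropenia:

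| Section 7.0 text | What it implies |
|---|---|
| ADR exemption | No individual report; later summary |
| SAE definition | Serious, because of the admission |
| IRB duty | Report within 24 hours |
| Drug supplier duty | Report within 24 hours |

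**Step 2. Reproduce the toxicity rule.** Inputs from Section 9.0: prior Beta(0.4, 0.6); stop if the posterior probability that p exceeds 0.40 is above 0.95; looks at 5, 10, 15, 20, 25 and 30 patients; maximum 35. With x toxic patients among n, the posterior is Beta(0.4 + x, 0.6 + n − x). The boundary is the smallest x that meets the criterion.

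| n | Boundary x | Posterior at x | Posterior at x − 1 |
|---|---|---|---|
| 5 | 4 | 0.958 | 0.796 |
| 10 | 7 | 0.968 | 0.889 |
| 15 | 10 | 0.979 | 0.935 |
| 20 | 12 | 0.961 | 0.906 |
| 25 | 15 | 0.976 | 0.943 |
| 30 | 17 | 0.965 | 0.926 |

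All six boundaries match the plan. The last column shows that one uncounted patient at the boundary reverses the decision at every look.

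**Step 3. Reproduce Table 2.** Add a Binomial(5, p) count at each look, remove the probability at or above the boundary, carry the rest forward, and sum what was removed. For example, at p = 0.60 the first look removes 5 × 0.6⁴ × 0.4 + 0.6⁵ = 0.337. The six looks give 0.337 + 0.134 + 0.076 + 0.135 + 0.043 + 0.075, or 0.802 before the terms are rounded.

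| True rate | Table 2 (simulated) | Exact |
|---|---|---|
| 0.20 | 0.006 | 0.007 |
| 0.30 | 0.039 | 0.040 |
| 0.40 | 0.152 | 0.157 |
| 0.50 | 0.447 | 0.447 |
| 0.60 | 0.808 | 0.802 |

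The largest difference is 0.006. The sample-size quartiles also match.

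**Step 4. Effect of missed patients.** The documents give no loss rate, so I assume that a fraction f of patients with countable toxicity is missed, with f from 10% to 50%. The boundaries count patients, so a patient is missed only if no other countable event is recorded for that patient. The counted rate is p(1 − f). For example, 0.60 × (1 − 0.20) = 0.48.

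| True rate | f = 0 | 10% | 20% | 30% | 50% |
|---|---|---|---|---|---|
| 0.50 | 0.447 | 0.279 | 0.157 | 0.081 | 0.018 |
| 0.60 | 0.802 | 0.597 | 0.375 | 0.200 | 0.040 |

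Entries are exact probabilities of stopping early. If nothing is missed, the first column stands.

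**The case against.** The strongest defense is that the SAE duties are unqualified, so the exemption should be read as limiting only non-serious ADR reports. That reading is possible, but the exemption names hospitalizations, which the SAE definition makes serious. Under the defense those words would do nothing. The text still needs reconciling, though one sentence might suffice.

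The second defense is that leaving an event out of individual ADR reports does not mean failing to capture it. This largely stands. Section 7.0 requires CRF entry and attribution, and Appendix D, which governs that entry, cannot be checked here. The stopping rule itself contains no exemption and is not tied to ADR reports. If the looks use complete CRF data, nothing is lost.

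Third, if the low dose does avoid myelosuppression, its complications should be few. That argues for the lower end of the assumed range, but the documents give no rate.

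Fourth, Section 8.0 says "Infection rates of influenza or Pneumococcal pneumonia will be recorded during the study". Those infections are therefore collected, but the sentence covers only those two conditions and does not connect them to grade or to the looks.

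A reader might also infer three stronger things that the documents do not support:

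- **That every infection or bleed is exempt.** The exemption covers only complications associated with myelosuppression. Low IgG is a different cause of infection.
- **That the stopping rule's protection is lost.** CRF capture may feed it fully.
- **That one particular fall applies**, such as Table 2's 0.808 to 0.152 at a true rate of 0.60. That requires the counted rate to drop from 0.60 to 0.40, a loss of 20/60 = 33% of toxic patients. Nothing in the documents singles out that share.

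**Conclusion.** The reporting conflict within Section 7.0 is explicit and needs no assumption. The mismatch between the exemption's rationale and the dose rationale in Section 2.0 is equally plain. Both bear on patient safety, so this goes beyond a missing detail.

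The effect on the toxicity monitor is conditional. It arises only if the looks rely on individual ADR reports, or if CRF entry under Appendix D follows the same exemption. The calculated falls show how sensitive the rule is over an assumed range of loss; they do not estimate what will happen. Even a 10% loss would matter: 0.447 to 0.279 at a true rate of 0.50 and 0.802 to 0.597 at 0.60. The boundaries and Table 2 are correct as they stand.

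**What to change.** 1. In Section 7.0, remove the exemption for this trial, or state that it never overrides SAE reporting to the IRB or the drug supplier.
2. Record each infection, bleed, febrile episode and related hospitalization individually in the CRF, with grade, date and attribution, and align Appendix D with this.
3. In Section 9.0 and the SAP, state that infection and bleeding of grade 3 or higher count as non-hematological toxicity whether or not linked to cytopenia, and name CRF adverse-event data as the source for each 5-patient look.

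The boundaries need no change. The cost is protocol wording and some extra data entry. The toxicity rule may trigger somewhat more often than it would on an incomplete count.

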6.0 Evaluation during the Study

Complete blood counts (white blood cell, hemoglobin, platelets and differential), serum chemistry, basic metabolic profile, (sodium, potassium, chloride, CO₂, BUN, creatinine and glucose) will be monitored once every two-four weeks (+/- 4 days) while on lenalidomide.

At 3 months (+/- 3 weeks), patients will have a physical examination, CBC with differential and chemical survey, serum beta-2-microglobulin and IgA, IgG, IgM levels, flow cytometry (CD4+, CD8+). Pregnancy tests for females of childbearing potential and Risks of Fetal Exposure, Pregnancy Testing Guidelines and Acceptable Birth Control Methods, will be discussed with the patients.

Pneumococcal vaccination: Serum levels of antipneumococcal capsular polysaccharide antibodies will be measured before, 4 weeks (+/- 2 week) and 3 months (+/- 3 weeks) after vaccination and at the end of the study (to assess sustainable antibody responses) by ELISA. Influenza vaccination: Haemagglutination inhibition antibody titres (HAI) will be assessed by WHO influenza reagent kit before, 4 weeks (+/- 2 week) and 3 months

(+/- 3 weeks) after vaccination and at end of the study (to assess sustainable antibody responses) [12]. Influenza specific quantitative and qualitative CD8+ and CD4+ T cell responses will be determined by multiparameter flow cytometry techniques from stored PBMC's from the patients before vaccination, 4 weeks (+/- 2 week) and 3 months (+/- 3 weeks) after vaccination [13, 14]. Serum samples for cytokine levels (properdin, IFN- γ , IL-10, TNF- α , BAFF, IL-8, CCL3, and CCL4) will be stored before influenza vaccination at 4 weeks (+/- 2 week), 3 months (+/- 3 weeks) and at the end of the study). PBMC's will be stored at baseline, 4 weeks (+/- 2 week) and 3 months (+/- 3 weeks) after influenza vaccination to determine by multiparameter flow cytometry technique changes in influenza specific quantitative (using HLA-A2 restricted FluMP pentamer) and qualitative (using CD107a, IFN-gamma, IL-2 and TNF-alpha by intracellular staining) CD8+ and CD4+ T cell responses, as described [15].

Criteria for study discontinuation:

Treatment with study drug is discontinued and the patient will be removed from study when any of the following occurs:

1. Lack of response
2. Adverse event(s) that in the judgment of the investigator or the patient may cause severe or permanent harm or which rule out continuation of the study drug
3. Withdrawal of consent
4. Lost to follow-up

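### The only myelosuppression reported as an individual ADR depends on a marrow result that is never scheduled and on absence of leukemia, so the exception would rarely apply in this CLL trial

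*Protocol*

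**What the plan says.** Protocol section 7.0 states that myelosuppression and associated fever, infection, bleeding and hospital admission "will not be reported as individual ADRs, but will be summarized in the updated and final reports". The reason given is that these events are expected and "are part of the treatment success (marrow emptying of leukemic cells". One exception follows: prolonged myelosuppression is to be reported as an ADR, and it is defined as "marrow cellularity <5% on day 42 or later (6 weeks) from start of therapy without evidence of leukemia". The same sentence says such cases feed into a maximum tolerated dose and dose-limiting toxicity.

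Section 2.0 gives a different view of the same toxicity: "The rationale for the low dose is the potential to obtain an immunoresponse while avoiding the risk for myelosuppression".

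For hematologic safety on treatment, section 6.0 schedules "Complete blood counts (white blood cell, hemoglobin, platelets and differential", together with chemistry, every two to four weeks while on drug. Section 7.0 grades hematologic toxicity by the 2008 IWCLL table, which uses platelets, hemoglobin and neutrophils.

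The Bayesian stopping rule in section 9.0 of the Protocol, repeated in the SAP, monitors toxicity "defined as any grade 3 or greater non-hematological toxicity".

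**The concern.** The exception is the only route by which myelosuppression becomes an individual ADR. It rests on a measurement that the trial does not plan to take, and on a disease state that many of these patients will not be in. It reads like a rule for a regimen meant to empty the marrow, whereas this trial gives a low dose for an immune effect.

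The low dose is justified by a claim about myelosuppression. That claim deserves review across patients while the trial is running. If the ADR rule hardly ever applies and the stopping rule does not count hematologic events, cytopenias that are not judged serious have no defined trial-level review before the updated and final summaries.

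**Working it through.** The plan gives no figure to reproduce. The check sets the relevant sections side by side.

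**1. Can the exception be met from planned data?**

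- *Marrow cellularity.* This needs a marrow sample. Section 3.0 lists immunoglobulins, vaccine antibodies and T-cell responses. Section 5.0 lists examination, ECG, blood counts, chemistry, beta-2-microglobulin, immunoglobulins, T-cell subsets and stored serum. Section 6.0 adds repeat blood tests, flow cytometry and stored cells. Section 8.0 uses IgG, titres and stored samples. Scheduled marrow examinations are 0 at baseline and 0 on study. Marrow is mentioned only in the drug background (2.0) and in the ADR paragraph itself (7.0).
- *Day 42.* At a two-week interval there are 42 / 14 = 3 scheduled blood counts by then. At a four-week interval 42 / 28 = 1.5, so there is one. These counts support IWCLL grading but cannot show cellularity.
- *No evidence of leukemia.* Inclusion criterion 1 admits untreated patients, and treated patients whatever their response. Untreated patients enter with leukemia. Some treated patients may be in remission and could satisfy this condition.

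All three must hold together, so the exception requires an unscheduled marrow in a patient without evidence of leukemia.

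**2. Does the rationale fit?** Section 7.0 treats myelosuppression as a sign of success; section 2.0 treats it as the risk that the dose is chosen to avoid. The two cannot both describe this trial. Section 7.0 also refers to a maximum tolerated dose and dose-limiting toxicity, which the plan does not otherwise define.

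**3. Where else is a cytopenia picked up?**

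| Route | Level | Covers persistent cytopenia? |
|---|---|---|
| Table 1, section 3.0 | Patient | Yes: dose hold and weekly counts |
| IWCLL grading, section 7.0 | Summary | Yes: graded and summarized |
| Case report form, section 7.0 | Record | Yes: adverse events entered, attribution assigned |
| SAE reporting, section 7.0 | Event | If serious: 24 hours, to the IRB and the drug supplier |
| Individual ADR, section 7.0 | Event | Only through the marrow exception |
| Stopping rule, section 9.0 and SAP | Trial | No: non-hematological only |

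**4. Illustrative size.** Rates of persistent grade 4 cytopenia are assumed, not taken from the documents. At 10%, 35 x 0.10 = 3.5 patients; at 30%, 35 x 0.30 = 10.5; so about 4 to 11. Without an unscheduled marrow, none would meet the ADR exception. At any rate, the cytopenia itself adds 0 to the count compared with the 40% boundary.

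**5. Inconsistencies that bear on any repair.**

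- *Hospital admission.* Section 7.0 exempts admissions linked to myelosuppression from individual reporting. It also makes inpatient admission an SAE criterion with a 24-hour deadline, and gives blood dyscrasias without admission as an example of an important medical event.
- *Grade 4 platelets.* Table 1 uses 25,000/mm³ or less, or 75% of baseline or less. The second limb is a fall of at least 100 - 75 = 25%, which is where IWCLL grade 2 begins (25-49%). The IWCLL table puts grade 4 at a 75% fall, which leaves 100 - 75 = 25% of baseline, or at a count below 20K.
- *Not evaluable.* The IWCLL footnotes exclude patients with pretreatment neutrophils below 1000 or platelets below 20K. Section 4.0 sets no minimum counts, so such patients can enrol.

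**The case against.** The strongest reply is that the other routes already do the work. Table 1 acts on grade 4 neutropenia and thrombocytopenia in each patient, adverse events go on the case report form, and serious events leave the site within 24 hours. Nothing forbids a marrow for cause, and the day 42 condition does not require a scheduled visit. Some enrolled patients may be in remission. Section 7.0 also defers to Appendices I and D, which were not available and may contain count-based rules. Restricting the stopping rule to non-hematological toxicity is an openly stated choice.

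Most of this stands. A reader might infer that the trial cannot detect persistent cytopenia, or cannot learn of it in time. The documents do not support that: blood counts are frequent, graded, recorded and acted on, and serious events are reported promptly. Nor does an absent marrow schedule prove that the exception would never be met.

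The reply does not rescue the reporting rule. Management of one patient and entry on a form are not review across patients. The SAE route is unclear where admissions are concerned, because section 7.0 points both ways. The scope of the stopping rule is not an error, but it means that the rule offers no backstop for hematologic events.

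**Conclusion.** The point holds in a limited form. The sole exception to the ADR exemption does not fit this trial: it needs an unscheduled marrow and absence of leukemia in a population enrolled with CLL, and its rationale contradicts the reason for the low dose. That it would rarely apply is an inference from the schedule and eligibility criteria, not a calculated rate.

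The consequence is a gap in individual ADR reporting and in trial-level review of hematologic toxicity that is not judged serious. The primary endpoint, the sample size and the 40% boundary are unaffected. The range of about 4 to 11 patients rests wholly on the assumed 10-30% rates and only shows scale. The conclusion also assumes that Appendices I and D contain no count-based reporting rule; if they do, the gap narrows, but section 7.0 would still need to agree with them. It is worth correcting by amendment because the correction is cheap and concerns the risk that the protocol itself names.

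**What to change.** - In section 7.0, replace the marrow, day 42 and MTD/DLT text with a definition of reportable myelosuppression based on the scheduled blood counts and the Protocol's IWCLL grades. The sponsor should set the grade threshold and the persistence period. Persistence needs a stated time unit, because counts are every two to four weeks routinely but weekly during a hold under Table 1.
- State how patients whom the IWCLL footnotes call not evaluable will be handled.
- Tabulate grade 3-4 hematologic toxicity beside the non-hematological count at each existing five-patient look, in both the Protocol and the SAP. Leave the 40% boundary unchanged.
- Reconcile the exemption for admissions linked to myelosuppression with the SAE criterion and the 24-hour rule.
- Reconcile the grade 4 platelet wording in Table 1 with the IWCLL table.
- Check the new text against Appendices I and D.

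The cost is amendment wording, one small table per look and some additional ADR reports; how many depends on the threshold chosen. No new test, visit or patient is needed.
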